## Chemistries

PARAMETER	GRADE 1 MILD	GRADE 2 MODERATE	GRADE 3 SEVERE	GRADE 4 POTENTIALLY LIFE- THREATENING
Calcium, High (mg/dL; mmol/L) ≥ 7 days of age	10.6 to < 11.5 2.65 to < 2.88	11.5 to < 12.5 2.88 to < 3.13	12.5 to < 13.5 3.13 to < 3.38	≥ 13.5 ≥ 3.38
< 7 days of age	11.5 to < 12.4 2.88 to < 3.10	12.4 to < 12.9 3.10 to < 3.23	12.9 to < 13.5 3.23 to < 3.38	≥ 13.5 ≥ 3.38
Calcium (Ionized), High (mg/dL; mmol/L)	> ULN to < 6.0 > ULN to < 1.5	6.0 to < 6.4 1.5 to < 1.6	6.4 to < 7.2 1.6 to < 1.8	≥ 7.2 ≥ 1.8
Calcium, Low (mg/dL; mmol/L) ≥ 7 days of age	7.8 to < 8.4 1.95 to < 2.10	7.0 to < 7.8 1.75 to < 1.95	6.1 to < 7.0 1.53 to < 1.75	< 6.1 < 1.53
< 7 days of age	6.5 to < 7.5 1.63 to < 1.88	6.0 to < 6.5 1.50 to < 1.63	5.50 to < 6.0 1.38 to < 1.50	< 5.50 < 1.38
Calcium (Ionized), Low (mg/dL; mmol/L)	< LLN to 4.0 < LLN to 1.0	3.6 to < 4.0 0.9 to < 1.0	3.2 to < 3.6 0.8 to < 0.9	< 3.2 < 0.8
Cardiac Troponin I, High	NA	NA	NA	Levels consistent with myocardial infarction or unstable angina as defined by the local laboratory
Creatine Kinase, High	3 to < 6 x ULN	6 to < 10x ULN	10 to < 20 x ULN	≥ 20 x ULN
Creatinine, High *Report only one	1.1 to 1.3 x ULN	> 1.3 to 1.8 x ULN OR Increase to 1.3 to < 1.5 x participant's baseline	> 1.8 to < 3.5 x ULN OR Increase to 1.5 to < 2.0 x participant's baseline	≥ 3.5 x ULN OR Increase of ≥ 2.0 x participant's baseline
Creatinine Clearance or eGFR, Low *Report only one	NA	< 90 to 60 ml/min or ml/min/1.73 m  OR 10 to < 30% decrease from participant's baseline	< 60 to 30 ml/min or ml/min/1.73 m  OR 30 to < 50% decrease from participant's baseline	< 30 ml/min or ml/min/1.73 m  OR ≥ 50% decrease from participant's baseline or dialysis needed
Glucose (mg/dL; mmol/L) Fasting, High	110 to 125 6.11 to < 6.95	> 125 to 250 6.95 to < 13.89	> 250 to 500 13.89 to < 27.75	≥ 500 ≥ 27.75
Nonfasting, High	116 to 160 6.44 to < 8.89	> 160 to 250 8.89 to < 13.89	> 250 to 500 13.89 to < 27.75	≥ 500 ≥ 27.75

 Use the applicable formula (i.e., Cockcroft-Gault in mL/min or Schwartz, MDRD, CKD-Epi in mL/min/1.73m^2). Sites should choose the method defined in their study and when not specified, use the method most relevant to the study population.

\*Reminder: Choose the method that selects for the higher grade.

## Chemistries

PARAMETER	GRADE 1 MILD	GRADE 2 MODERATE	GRADE 3 SEVERE	GRADE 4 POTENTIALLY LIFE- THREATENING
Glucose, Low (mg/dL; mmol/L) ≥ 1 month of age	55 to 64 3.05 to <3.55	40 to <55 2.22 to < 3.05	30 to <40 1.67 to < 2.22	< 30 < 1.67
< 1 month of age	50 to 54 2.78 to < 3.00	40 to < 50 2.22 to < 2.78	30 to < 40 1.67 to < 2.22	< 30 < 1.67
Lactate, High	ULN to < 2.0 x ULN without acidosis	≥ 2.0 x ULN without acidosis	Increased lactate with pH < 7.3 without life- threatening consequences	Increased lactate with pH < 7.3 with life- threatening consequences
Lipase, High	1.1 to < 1.5 x ULN	1.5 to < 3.0 x ULN	3.0 to < 5.0 x ULN	≥ 5.0 x ULN
Lipid Disorders (mg/dL; mmol/L)				
Cholesterol, Fasting, High ≥ 18 years of age	200 to < 240 5.18 to < 6.19	240 to < 300 6.19 to < 7.77	≥ 300 ≥ 7.77	NA
< 18 years of age	170 to < 200 4.40 to < 5.15	200 to < 300 5.15 to < 7.77	≥ 300 ≥ 7.77	NA
LDL, Fasting, High ≥ 18 years of age	130 to < 160 3.37 to < 4.12	160 to < 190 4.12 to < 4.90	≥ 190 ≥ 4.90	NA
> 2 to < 18 years of age	110 to < 130 2.85 to < 3.34	130 to < 190 3.34 to < 4.90	≥ 190 ≥ 4.90	NA
Triglycerides, Fasting, High	150 to 300 1.71 to 3.42	>300 to 500 >3.42 to 5.7	>500 to <1,000 >5.7 to 11.4	> 1,000 > 11.4
Magnesium^15, Low (mEq/L; mmol/L)	1.2 to < 1.4 0.60 to < 0.70	0.9 to < 1.2 0.45 to < 0.60	0.6 to < 0.9 0.30 to < 0.45	< 0.6 < 0.30
Phosphate, Low (mg/dL; mmol/L) > 14 years of age	2.0 to < LLN 0.65 to < LLN	1.4 to < 2.0 0.45 to < 0.65	1.0 to < 1.4 0.32 to < 0.45	< 1.0 < 0.32
1 to 14 years of age	3.0 to < 3.5 0.97 to < 1.13	2.5 to < 3.0 0.81 to < 0.97	1.5 to < 2.5 0.48 to < 0.81	< 1.5 < 0.48
< 1 year of age	3.5 to < 4.5 1.13 to < 1.45	2.5 to < 3.5 0.81 to < 1.13	1.5 to < 2.5 0.48 to < 0.81	< 1.5 < 0.48
Potassium, High (mEq/L; mmol/L)	5.6 to < 6.0 5.6 to < 6.0	6.0 to < 6.5 6.0 to < 6.5	6.5 to < 7.0 6.5 to < 7.0	≥ 7.0 ≥ 7.0
Potassium, Low (mEq/L; mmol/L)	3.0 to < 3.4 3.0 to < 3.4	2.5 to < 3.0 2.5 to < 3.0	2.0 to < 2.5 2.0 to < 2.5	< 2.0 < 2.0

 To convert a magnesium value from mg/dL to mmol/L, laboratories should multiply by 0.4114.

## Chemistries

PARAMETER	GRADE 1 MILD	GRADE 2 MODERATE	GRADE 3 SEVERE	GRADE 4 POTENTIALLY LIFE- THREATENING
Sodium, High (mEq/L; mmol/L)	146 to < 150 146 to < 150	150 to < 154 150 to < 154	154 to < 160 154 to < 160	≥ 160 ≥ 160
Sodium, Low (mEq/L; mmol/L)	130 to < 135 130 to < 135	125 to < 130 125 to < 130	121 to < 125 121 to < 125	≤ 120 ≤ 120
Uric Acid, High (mg/dL; mmol/L)	7.5 to < 10.0 0.45 to < 0.59	10.0 to < 12.0 0.59 to < 0.71	12.0 to < 15.0 0.71 to < 0.89	≥ 15.0 ≥ 0.89

## Hematology

PARAMETER	GRADE 1 MILD	GRADE 2 MODERATE	GRADE 3 SEVERE	GRADE 4 POTENTIALLY LIFE- THREATENING
Absolute CD4+ Count, Low (cell/mm  ; cells/L) > 5 years of age (not HIV infected)	300 to < 400 300 to < 400	200 to < 300 200 to < 300	100 to < 200 100 to < 200	< 100 < 100
Absolute Lymphocyte Count, Low (cell/mm  ; cells/L) > 5 years of age (not HIV infected)	600 to < 650 0.600 x 10^9 to < 0.650 x 10^9	500 to < 600 0.500 x 10^9 to < 0.600 x 10^9	350 to < 500 0.350 x 10^9 to < 0.500 x 10^9	< 350 < 0.350 x 10^9
Absolute Neutrophil Count (ANC), Low (cells/mm  ; cells/L) > 7 days of age	800 to 1,000 0.800 x 10^9 to 1.000 x 10^9	600 to 799 0.600 x 10^9 to 0.799 x 10^9	400 to 599 0.400 x 10^9 to 0.599 x 10^9	< 400 < 0.400 x 10^9
2 to 7 days of age	1,250 to 1,500 1.250 x 10^9 to 1.500 x 10^9	1,000 to 1,249 1.000 x 10^9 to 1.249 x 10^9	750 to 999 0.750 x 10^9 to 0.999 x 10^9	< 750 < 0.750 x 10^9
≤ 1 day of age	4,000 to 5,000 4.000 x 10^9 to 5.000 x 10^9	3,000 to 3,999 3.000 x 10^9 to 3.999 x 10^9	1,500 to 2,999 1.500 x 10^9 to 2.999 x 10^9	< 1,500 < 1.500 x 10^9
Fibrinogen, Decreased (mg/dL; g/L)	100 to < 200 1.00 to < 2.00 OR 0.75 to < 1.00 x LLN	75 to < 100 0.75 to < 1.00 OR ≥ 0.50 to < 0.75 x LLN	50 to < 75 0.50 to < 0.75 OR 0.25 to < 0.50 x LLN	< 50 < 0.50 OR < 0.25 x LLN OR Associated with gross bleeding
Hemoglobin, Low (g/dL; mmol/L)  ≥ 13 years of age (male only)	10.0 to 10.9 6.19 to 6.76	9.0 to < 10.0 5.57 to < 6.19	7.0 to < 9.0 4.34 to < 5.57	< 7.0 < 4.34
≥ 13 years of age (female only)	9.5 to 10.4 5.88 to 6.48	8.5 to < 9.5 5.25 to < 5.88	6.5 to < 8.5 4.03 to < 5.25	< 6.5 < 4.03

 Male and female sex are defined as sex at birth. For transgender participants ≥13 years of age who have been on hormone therapy for more than 6 consecutive months, grade hemoglobin based on the gender with which they identify (i.e., a transgender female should be graded using the female sex at birth hemoglobin laboratory values).

 The most commonly used conversion factor to convert g/dL to mmol/L is 0.6206. For grading hemoglobin results obtained by an analytic method with a conversion factor other than 0.6206, the result must be converted to g/dL using appropriate conversion factor for the particular laboratory.

## Hematology

PARAMETER	GRADE 1 MILD	GRADE 2 MODERATE	GRADE 3 SEVERE	GRADE 4 POTENTIALLY LIFE- THREATENING
57 days of age to < 13 years of age (male and female)	9.5 to 10.4 5.88 to 6.48	8.5 to < 9.5 5.25 to < 5.88	6.5 to < 8.5 4.03 to < 5.25	< 6.5 < 4.03
36 to 56 days of age (male and female)	8.5 to 9.6 5.26 to 5.99	7.0 to < 8.5 4.32 to < 5.26	6.0 to < 7.0 3.72 to < 4.32	< 6.0 < 3.72
22 to 35 days of age (male and female)	9.5 to 11.0 5.88 to 6.86	8.0 to < 9.5 4.94 to < 5.88	6.7 to < 8.0 4.15 to < 4.94	< 6.7 < 4.15
8 to ≤ 21 days of age (male and female)	11.0 to 13.0 6.81 to 8.10	9.0 to < 11.0 5.57 to < 6.81	8.0 to < 9.0 4.96 to < 5.57	< 8.0 < 4.96
≤ 7 days of age (male and female)	13.0 to 14.0 8.05 to 8.72	10.0 to < 13.0 6.19 to < 8.05	9.0 to < 10.0 5.59 to < 6.19	< 9.0 < 5.59
INR, High (not on anticoagulation therapy)	1.1 to < 1.5 x ULN	1.5 to < 2.0 x ULN	2.0 to < 3.0 x ULN	≥ 3.0 x ULN
Methemoglobin (% hemoglobin)	5.0 to < 10.0%	10.0 to < 15.0%	15.0 to < 20.0%	≥ 20.0%
PTT, High (not on anticoagulation therapy)	1.1 to < 1.66 x ULN	1.66 to < 2.33 x ULN	2.33 to < 3.00 x ULN	≥ 3.00 x ULN
Platelets, Decreased (cells/mm  ; cells/L)	100,000 to < 125,000 100.000 x 10^9 to < 125.000 x 10^9	50,000 to < 100,000 50.000 x 10^9 to < 100.000 x 10^9	25,000 to < 50,000 25.000 x 10^9 to < 50.000 x 10^9	< 25,000 < 25.000 x 10 
PT, High (not on anticoagulation therapy)	1.1 to < 1.25 x ULN	1.25 to < 1.50 x ULN	1.50 to < 3.00 x ULN	≥ 3.00 x ULN
WBC, Decreased (cells/mm  ; cells/L)				
> 7 days of age	2,000 to 2,499 2.000 x 10^9 to 2.499 x 10^9	1,500 to 1,999 1.500 x 10^9 to 1.999 x 10^9	1,000 to 1,499 1.000 x 10^9 to 1.499 x 10^9	< 1,000 < 1.000 x 10 
≤ 7 days of age	5,500 to 6,999 5.500 x 10^9 to 6.999 x 10^9	4,000 to 5,499 4.000 x 10^9 to 5.499 x 10^9	2,500 to 3,999 2.500 x 10^9 to 3.999 x 10^9	< 2,500 < 2.500 x 10 

## Urinalysis

PARAMETER	GRADE 1 MILD	GRADE 2 MODERATE	GRADE 3 SEVERE	GRADE 4 POTENTIALLY LIFE- THREATENING
Glycosuria (random collection tested by dipstick)	Trace to 1+ or ≤ 250 mg	2+ or > 250 to ≤ 500 mg	> 2+ or > 500 mg	NA
Hematuria (not to be reported based on dipstick findings or on blood believed to be of menstrual origin)	6 to < 10 RBCs per high power field	≥ 10 RBCs per high power field	Gross, with or without clots OR With RBC casts OR Intervention indicated	Life-threatening consequences
Proteinuria (random collection tested by dipstick)	1+	2+	3+ or higher	NA

### 11.3. Appendix 3: Liver Safety – Required actions, Follow up Assessments and Study Treatment Restart Guidelines

#### 11.3.1. VSLC Guidelines for Drug Restart after stop for Liver criteria

**Drug Restart** refers to resuming study treatment following liver events meeting stopping criteria **in which there is a clear underlying cause (other than DILI) of the liver event (e.g., biliary obstruction, pancreatic events, hypotension, acute viral hepatitis).**

Furthermore, there should be no evidence of alcoholic hepatitis or hypersensitivity, and the drug should not be associated with HLA markers of liver injury. (Table 12; Figure 17).

**Restarts should be limited to cases in which there is clear evidence that the underlying cause of the liver event is not related to study drug.**

#### DRUG RESTART

“Drug restart” can be approved by the VSLC for **transient, defined non-drug-induced** liver injury if no evidence of:

- immunoallergic injury /HLA association with injury
- alcoholic hepatitis

Study drug must be held while labs and evaluation are completed to assess diagnosis.

#### 11.3.2. VSLC Decision Process for Drug Restart Approval or Disapproval

[figure not shown]
- Principal Investigator (PI) requests consideration of drug re-initiation for a participant stable or improving on IP, who exhibits liver chemistry elevation meeting participant stopping criteria, which is transient, non-drug-related, and liver chemistries have improved to normal or are within 1.5x baseline and ALT < 5xULN.
- GSK Medical Monitor and GCSP Physician to review the participant’s diagnosis restart risk factors (Hepatotoxicity Panel consultation is available) and complete checklist (Table 12).
  - *must present source data defining the patient’s current resistance profile with documented evidence of extensive drug resistance and previous drug history.*
- The local operating company (LOC) medical director should be informed that study drug restart is under consideration and of the final decision, whether or not to proceed.
- Relevant physicians (listed below) must review and agree on action to be taken regarding request for drug restart:

- Safety Review Team Leader, Safety Development Leader, or Senior Safety Physician
- MDL and PPL Request is taken to VSLC for final decision

**Table 12 Checklist for Phase III drug restart after well-explained liver injury (e.g. biliary, pancreatic, hypotensive events, congestive heart failure (CHF), acute viral hepatitis), and improvement of liver chemistry to normal or  $\leq 1.5x$  baseline & ALT  $< 5x$  ULN**

	Yes	No
Is participant stable or improving on IP?		
Do not restart if the following risk factors at initial liver injury:		
fever, rash, eosinophilia, or hypersensitivity		
drug-induced liver injury		
alcoholic hepatitis (AST > ALT, typically $< 10x$ ULN)		
IP has an HLA genetic marker associated with liver injury (e.g. lapatinib, abacavir, amoxicillin/clavulanate)		
Source data defining the patients current resistance profile		
Previous drug history		

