***Drug Restart Following Transient Resolving Liver Events Not Related to Study Drug***

Approval by VSLC for drug restart can be considered where:

Liver chemistries have a clear underlying cause (e.g., biliary obstruction, hypotension, and liver chemistries have improved to normal or are within  $1.5 \times$  baseline and  $ALT < 3 \times ULN$ ). Ethics Committee or IRB approval of drug restart must be obtained, as required.

If restart of drug is approved by VSLC in writing, the participant must be provided with a clear description of the possible benefits and risks of drug administration, including the possibility of recurrent, more severe liver injury or death.

The participant must also provide signed informed consent specifically for the restart. Documentation of informed consent must be recorded in the study chart.

Study drug must be administered at the dose specified by VSLC.

Participants approved by VSLC for restarting study drug must return to the clinic once a week for liver chemistry tests for a minimum of one month and thereafter for as long as clinically indicated and then laboratory monitoring may resume as per protocol. If protocol defined stopping criteria for liver chemistry elevations are met, study drug must be stopped.

Refer to Section 11.2, U.S. Department of Health and Human Services, National Institutes of Health, National Institute of Allergy and Infectious Diseases, Division of AIDS. Division of AIDS (DAIDS, 2017) Table for Grading the Severity of Adult and Pediatric Adverse Events, Version 2.1. [March 2017]. Available from: <https://rsc.tech-res.com/docs/default-source/safety/daids-ae-grading-table-mar2017.pdf>

Refer to Section 11.3, Appendix 3: Liver Safety – Required actions, Follow up Assessments and : Liver Safety – Study Treatment Restart Guidelines for further details.

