20. Ongoing malignancy other than cutaneous Kaposi's sarcoma, basal cell carcinoma, or resected, non-invasive cutaneous squamous cell carcinoma, or cervical intraepithelial neoplasia; other localized malignancies require agreement between the investigator and the Study medical monitor for inclusion of the participant prior to randomization.
21. Any condition which, in the opinion of the Investigator, may interfere with the

absorption, distribution, metabolism or excretion of the study drugs or render the participant unable to receive study medication.
 
22. History or presence of allergy or intolerance to the study drugs or their components or drugs of their class. In addition, if heparin is used during PK sampling, participants with a history of sensitivity to heparin or heparin-induced thrombocytopenia must not be enrolled.
 
23. Current or anticipated need for chronic anti-coagulation with the exception of the use of low dose acetylsalicylic acid (<math>\leq 325</math> mg) or hereditary coagulation and platelet disorders such as haemophilia or Von Willebrand Disease.

A2M parent study - Exclusionary Laboratory Values or Clinical Assessments at Screening (a single repeat to determine eligibility is allowed)

24. Any verified Grade 4 laboratory abnormality. A single repeat test is allowed during the Screening phase to verify a result.
 
25. Any acute laboratory abnormality at Screening, which, in the opinion of the investigator, would preclude the participant's participation in the study of an investigational compound.
 
26. Participant has estimated creatine clearance <math>< 50</math> mL/min per <math>1.73\text{m}^2</math> via Chronic Kidney Disease-Epidemiology Collaboration (CKD-EPI) Method.
 
27. Alanine aminotransferase (ALT) <math>\geq 3 \times</math> ULN at Screening.

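### Two different ALT ceilings, below 3 × ULN and below 5 × ULN, are given for approving the same restart of study drug after a liver event

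*Protocol*

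**What the plan says.** The body has a restart passage under the heading "Drug Restart Following Transient Resolving Liver Events Not Related to Study Drug", printed between Sections 7.4.5.6 and 7.4.5.7. It opens with "Approval by VSLC for drug restart can be considered where" and then lists the conditions: a clear underlying cause, "and liver chemistries have improved to normal or are within" 1.5 × baseline, and ALT below 3 × ULN. It closes by sending the reader to Appendix 3 for more detail.

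Appendix 3 deals with the same restart. Section 11.3.1 says that it "can be approved by the VSLC for transient, defined non-drug-induced liver injury if no evidence of" immunoallergic injury or alcoholic hepatitis. Section 11.3.2 describes the investigator's request and sets the condition that "liver chemistries have improved to normal or are within 1.5x baseline and ALT < 5xULN". The medical monitor and a safety physician then complete Table 12, titled "Checklist for Phase III drug restart after well-explained liver injury". The rest of that title repeats the 1.5 × baseline condition and the ceiling of 5 × ULN.

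**The concern.** The two texts agree on who decides (the VSLC), on the situation (a transient liver event with a known cause other than study drug) and on the companion condition (normal, or within 1.5 × baseline). Only the ALT ceiling differs. A site that starts from the body is sent to an appendix with another number, and the checklist completed for the decision carries that other number.

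This is a gate on giving the drug again after a liver event. Section 11.3.3.2 requires a new consent that warns of more severe liver injury or death. With two ceilings, two participants with the same values can be handled differently, and a restart that satisfies Appendix 3 can be a deviation from the body text.

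**Working it through.** No planned figure has to be reproduced here. The check sets the two rules side by side and finds where they give different answers.

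| | Body restart passage | Section 11.3.2 and Table 12 title |
|---|---|---|
| Decision | VSLC approval of restart | VSLC approval of restart |
| Event | Transient, not drug-related | Transient, not drug-related |
| Chemistries | Normal or within 1.5 × baseline | Normal or within 1.5 × baseline |
| ALT ceiling | < 3 × ULN | < 5 × ULN |

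**Inputs.** The two ceilings and the 1.5 × baseline condition come from the passages in the table. A bound on baseline comes from Section 11.13.4.1, which lists ALT of 3 × ULN or more at screening among the parent-study exclusions. I assume that the baseline ALT used in the restart rule is also below 3 × ULN.

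**Formula.** Let *a* be current ALT and *b* baseline ALT, both in multiples of ULN. If ALT is normal, both rules are met. Otherwise:

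- body: *a* ≤ 1.5*b* and *a* < 3
- appendix: *a* ≤ 1.5*b* and *a* < 5

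The rules differ where 3 ≤ *a* < 5 and *a* ≤ 1.5*b*.

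**Results.**

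1. An ALT of 3 or more can pass the shared condition only if 1.5*b* ≥ 3, that is *b* ≥ 3 / 1.5 = 2. With baseline below 2 × ULN the two rules always agree.
2. With *b* < 3, 1.5*b* < 4.5. The conflict is then baseline 2 to below 3 × ULN with current ALT 3 to below 4.5 × ULN.
3. Example: *b* = 2.5 and *a* = 3.5. The shared limit is 1.5 × 2.5 = 3.75, which is met. Since 3.5 < 5 the appendix is satisfied; since 3.5 ≥ 3 the body is not.
4. Range: if baseline were not bounded at 3, the top of the band would be reached at *b* = 5 / 1.5 = 3.33. If the 1.5 × baseline condition is read as not applying to ALT itself, the conflict is the whole range from 3 to below 5 × ULN.

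**Effect on the analysis.** Under Section 9.3.1, a participant without evaluable data who discontinues counts as HIV-1 RNA ≥ 50 c/mL only if the reason is not an adverse event and the RNA at discontinuation is ≥ 50 c/mL, or after a treatment change that the protocol does not permit. Stopping for a liver adverse event would not ordinarily add a primary failure. Under Section 9.3.2.1 it could add one non-responder to the key secondary endpoint. One participant in 510 is 1 / 510 = 0.2 percentage points, against margins of 4 points (primary) and 10 points (key secondary).

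**The case against.** The strongest defence is that the figures belong to successive steps: Section 11.3.2 says when an investigator may ask, and the body says when the committee may approve. A case could then pass the request limit and still be held to the approval limit. The documents do not say this. Table 12 attaches the higher figure to the restart checklist itself, and the body refers to Appendix 3 for detail, not for a different step.

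A second defence is that no ALT value alone leads to a restart. This stands. The medical monitor and safety physicians review the case, the VSLC decides, ethics approval is obtained as required, consent is specific to the restart, and liver chemistries follow weekly for at least a month. The mismatch affects which cases may go forward to the committee; it does not produce automatic restarts.

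A third is that only part of the protocol is at hand. Section 5.5.1.4.2, which the Amendment 5 log names as covering the same topic, and Figure 17 are not shown, and either might indicate which figure controls. That limits any statement about precedence. It does not remove the disagreement between the two texts that are shown, neither of which belongs to the amendment log.

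A reader might also infer that every participant with ALT between 3 and 5 × ULN is treated differently, or that the mismatch could bias the primary result. The 1.5 × baseline condition contradicts the first unless it is read loosely, and the snapshot rules do not support the second.

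**Conclusion.** The contradiction is real in the current text and has to be resolved, because a safety rule with two thresholds cannot be followed consistently. Its reach is narrow: baseline ALT of at least 2 × ULN and, in practice, current ALT from 3 to below 4.5 × ULN. That zone rests on applying the 1.5 × baseline condition to ALT and on the screening exclusion also bounding baseline. The number of participants in it cannot be computed from the protocol but is likely to be small. There is no material effect on the primary endpoint, and none on sample size, power or type I error. Nothing here implies which of the two ceilings is the right one.

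**What to change.** Reconcile the body restart passage, Section 11.3.2 and the Table 12 title to a single ALT limit chosen by the sponsor's hepatic safety experts. Check Section 5.5.1.4.2 and Figure 17 against it. State the limit once and let the other places cross-refer to it. If separate limits for request and approval are intended, say so and label each. In the same edit, make explicit whether the 1.5 × baseline condition applies to ALT itself, since that decides how wide the disagreement is.

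The cost is a wording correction in the next amendment and a notice to sites and medical monitors. No analysis, sample size or data collection changes.

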### 7.7.1. HIV-1 Polymerase Viral Genotyping and Phenotyping

Participants meeting confirmed virologic failure will have plasma samples tested for HIV-1 PRO and RT genotype and phenotype and HIV-1 integrase genotype and phenotype from samples collected at the time of meeting suspected virologic failure; these results will be reported to the investigator as soon as available to provide guidance for election of an alternative regimen.

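### The ALT limit for restarting study drug after a non-drug-related liver event is below 3×ULN in the Section 7.4.5 restart text but below 5×ULN in Appendix 3

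*Protocol*

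**What the plan says.** The restart text within Section 7.4.5 (the block on transient resolving liver events not related to study drug, placed just before Section 7.4.5.7) opens with "Approval by VSLC for drug restart can be considered where". It then gives a clear underlying cause, chemistries that are normal or within 1.5 times baseline, and ALT below 3×ULN. It ends by sending the reader to Appendix 3: "Study Treatment Restart Guidelines for further details".

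Appendix 3, Section 11.3.2, describes the route to the VSLC decision. The investigator may request restart for a transient, non-drug-related elevation once "liver chemistries have improved to normal or are within 1.5x baseline and ALT < 5xULN". Sponsor physicians then complete Table 12, whose title begins "Checklist for Phase III drug restart after well-explained liver injury" and ends with the same baseline condition and ALT below 5×ULN. After that the request goes to the VSLC.

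The approval statement in Section 11.3.1 gives no ALT figure. It lists conditions that rule restart out, such as "immunoallergic injury /HLA association with injury" and alcoholic hepatitis.

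**The concern.** The restart text and Appendix 3 concern the same committee, the same kind of event and the same recovery rule relative to baseline. Only the ALT number differs. An investigator working from Section 7.4.5 would hold back a participant whom an investigator working from Section 11.3.2 would put forward, and the sponsor's own checklist would support the second.

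The protocol requires that participants be told restart may bring back a more severe liver injury or death. A threshold for that decision should be a single number, applied alike at every site and in both arms.

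**Working it through.** No figure in the plan needs reproducing. The check compares the texts and then finds where the two limits lead to different decisions.

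**The three statements side by side**

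| Place | Relative condition | ALT limit |
|---|---|---|
| Section 7.4.5 restart text | normal or within 1.5 × baseline | < 3×ULN |
| Section 11.3.2, investigator request | normal or within 1.5 × baseline | < 5×ULN |
| Section 11.3.2, Table 12 title | normal or ≤ 1.5 × baseline | < 5×ULN |

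**Other inputs**

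- Parent-study exclusion of ALT ≥ 3×ULN at Screening, as repeated in the sub-study criteria (Section 11.13.4.1.2, criterion 27).
- ALT Grade 2 is 2.5 to < 5.0×ULN (Appendix 2, Chemistries).

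**Formula.** Let b be baseline ALT in multiples of ULN. The highest recovered ALT compatible with restart is

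ceiling(b) = min{ max(1.0, 1.5b), cap },

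with cap = 3 in Section 7.4.5 and cap = 5 in Appendix 3. The ALT caps themselves are strict inequalities.

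**Where the texts part**

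- The lower cap starts to bind at b = 3 / 1.5 = 2.0. Below that baseline the relative condition is the tighter one and both texts give the same answer.
- The higher cap starts to bind at b = 5 / 1.5 = 3.33.
- If baseline is below 3.0×ULN, the Appendix 3 ceiling stays below 1.5 × 3.0 = 4.5×ULN.

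| Baseline b (×ULN) | 1.5b | Section 7.4.5 ceiling | Appendix 3 ceiling | Gap |
|---|---|---|---|---|
| 1.0 | 1.5 | 1.5 | 1.5 | 0 |
| 1.5 | 2.25 | 2.25 | 2.25 | 0 |
| 2.25 | 3.375 | 3.0 | 3.375 | 0.375 |
| 2.5 | 3.75 | 3.0 | 3.75 | 0.75 |
| 2.75 | 4.125 | 3.0 | 4.125 | 1.125 |

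With baseline below the screening exclusion, the disputed cases are therefore baseline 2.0 to < 3.0×ULN with recovered ALT 3.0 to < 4.5×ULN, all of them Grade 2. If baseline ALT could exceed the screening limit, the disputed range widens to 3.0 to < 5.0×ULN.

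**The case against.** The best defence is a two-stage reading: 5×ULN governs submission and 3×ULN governs approval. The request and the checklist do come before the VSLC decides, and the Table 12 limit stands in its title, not in a row to be ticked. This reading cannot be ruled out completely, because Section 5.5.1 and Figure 17 are not available here. But nothing in the text shown sets up two stages, and no visible step in Appendix 3 applies 3×ULN. If two stages were meant, the protocol should say so.

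The Section 7.4.5 sentence is also loosely punctuated: the ALT limit falls inside a parenthesis of examples. That weakens its form, but it is hard to read the limit as anything other than a condition.

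It is also fair to say that safeguards apply under either number: a clear non-drug cause, written VSLC approval, ethics approval as required, fresh consent, weekly liver chemistries for at least a month, and continued stopping criteria. These keep the point minor without removing the contradiction.

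A reader might infer two stronger things, and the documents support neither.

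- *That Appendix 3 wrongly adds a resistance condition.* The sub-bullet under the checklist step asks for source data on the "current resistance profile with documented evidence of extensive drug resistance and previous drug history", while Table 12 lists only the resistance profile and drug history. The sub-bullet can be read as the fuller form of those rows, or as a deliberate restriction. Nor can it be said that suppressed participants could have no such evidence. Section 7.7.1 states that "Participants meeting confirmed virologic failure will have plasma samples tested for HIV-1 PRO and RT genotype and phenotype", but Section 7.7.2 also allows testing of baseline PBMC and stored samples. An error is not established.
- *That the disputed ALT values amount to the protocol's serious liver injury.* The definition in Section 11.6.2 needs raised bilirubin or INR in addition to ALT ≥ 3×ULN. ALT alone does not meet it.

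**Conclusion.** The contradiction stands in the current text: below 3×ULN in one place and below 5×ULN in two, for one decision. It is an internal inconsistency in a liver-safety threshold and worth correcting, but its reach is narrow. It changes the answer only for baseline ALT of about 2.0×ULN or more, and then for recovered ALT of 3.0 to below 4.5×ULN, provided baseline remains under the screening exclusion. The protocol gives no count of expected restart requests; that few participants are affected is a judgement from the combination required (raised baseline, a non-drug-related stopping event, incomplete recovery). Endpoint, power and primary analysis are untouched. Which limit was intended cannot be settled without Section 5.5.1.

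**What to change.** State one ALT limit in the Section 7.4.5 restart text, the Section 11.3.2 request bullet and the Table 12 title, and make it agree with Section 5.5.1. Use below 3×ULN unless the sponsor gives a reason for below 5×ULN. If different limits for submission and approval are intended, label them as such.

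Leave the resistance wording as it is. At most, ask the sponsor to confirm whether extensive resistance is meant as a condition for restart.

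The change is one number aligned in three places, with no new procedures or data. The downside of the stricter limit is that a few participants with baseline ALT of about 2.0×ULN or more may wait longer to restart or be unable to.
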